Effects of a Numerical Superiority and Inferiority Tactical Training Program Compared to
Conventional Training on Procedural Tactical Knowledge and Executive Functions in
Soccer Players. A Randomized Controlled Trial

Date: September 9th, 2023

Protocol

There is a great need to establish reliable evaluation and intervention protocols to improve the tactical component, decision making (TD) and procedural tactical knowledge (PTK) in Soccer.

Objectives

To determine the effects of a tactical training program of numerical superiority and inferiority during 12 weeks of follow-up on the PTK, which will be evaluated by calculating offensive, defensive and global effectiveness indices (EI) of 24 male amateur soccer players, as well as the effect on their executive functions.

Type of study

The study corresponds to a predominantly quantitative approach. According to Friedman et al., (2010) it is a prospective, experimental study, in parallel, with 2 randomized groups (experimental and control). The study is a repeated measures design because measurements of the most important outcomes (primary and secondary) will be performed at four times: pretest (week 1), intermediate test 1 (week 6), intermediate test 2 (week 11) and posttest (week 16).

Site Selection (Context and Access)

The study is being carried out with soccer players from a club that competes in the Antioquia Soccer League who train on fields in the city of Medellín, which are made of synthetic grass and natural grass. These fields are in good condition and offer adequate technical conditions and security for soccer players.

Population

The investigation is being carried out with amateur soccer players, male, in the First B departmental category.

Selection criteria

Inclusion criteria

Soccer players belonging to a soccer club.

Soccer players playing roles of outfield (all except goalkeepers).

They compete in the First B category of the Antioquia Football League in the 2023 season.

Players aged between 17 and 26 years.

Players with at least six months of experience in federated soccer.

Players who do not present cognitive disorders that make learning difficult, which can be identified through monitoring by the coaches and/or tests carried out by the Neuropsychology staff.

They must be affiliated to the health system of the contributory or subsidized regime.

They must agree to participate in the study after knowing and signing the consent or informed assent as appropriate.

Exclusion criteria

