
Players with musculoskeletal disorders at the time of sample selection.

Players recovering from injury.

Sample Size Calculation

A systematic probabilistic sampling of permuted blocks was carried out, for which the Epidat software, V. 4.2, was used. Taking into account the study by Sierra-Ríos et al., (2020) in which they report a mean difference of 1.13 and a standard deviation of 0.81, 5 scenarios were established to calculate the sample size (with powers of 80, 85, 90, 95 and 99%). Based on these five scenarios, the samples found are:

Scenario 1 (80% power): (20 soccer players. GE = 10 and GC = 10).

Scenario 2 (85% power): (22 soccer players. GE = 11 and GC = 11).

Scenario 3 (90% power): (24 soccer players. GE = 12 and GC = 12).

Scenario 4 (95% power): (30 soccer players. GE = 15 and GC = 15).

Scenario 5 (99% power): (40 soccer players. GE = 20 and GC = 20).

Based on these results of the calculation of different sample sizes, it decided to work with scenario 3 described above.

Randomization Process

To carry out the randomization sequence generation method, a sequence of permuted blocks of 4, 6 was generated. The relationship between groups is 1:1, for which the random assignment software (simulation) was used <https://www.sealedenvelope.com/simple-randomiser/v1/lists>.

The allocation was concealed by means of sealed and opaque envelopes, for which the 24 envelopes were available for each one of the participants. The envelopes were numbered from 1 to 24, the name of each research participant was added to them along with a sheet of carbon paper and the name of each research participant was marked for each intervention experimental group (GE) and control group (GC). This process of randomization sequence generation, allocation concealment, and allocation was performed by someone other than the research staff.

Variables

The study's variables, their operationalization, function, nature, measurement scales, units of measurement and instruments used are described in Table 1.

Table 1. Variables and their operationalization

Variable	Function	Nature	Scale	Unit of measurement/values	Instrument
PTK (Offensive IE)	Dependent	Quantitative	Discrete, interval Continuos, Ratio	Volumen (N° of times the action is performed) IE (*formula)	FOCOS
PTK (IE Defensive)	Dependent	Quantitative	Discrete, interval Continuos, Ratio	Volumen N° of times the action is performed) IE (**formula)	FOCOS

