research protocol, that is, pretest (week 1), intermediate test 1 (week 6), test intermediate 2 (week 11) and posttest (week 16). Likewise, the groups formed randomly and the confrontation between them determined by chance at all test will be respected. If for any reason a participant cannot take the test due to any circumstance (absence at the session, physical discomfort, momentary bruises, injury or unexpected situations), his replacement will be arranged with IUEFD student with experience as soccer players and who previously know the protocol to complete the gap, or with soccer players who are on trial at the club and who are not part of the comparison groups. The tests will be carried out on Wednesday from 6 to 8 in the morning in the respective weeks (1, 6, 11 and 16).

Once the tests have been completed and duly filmed, the respective videos will be passed on to the evaluator (video analyst) who will download the videos, analyze the different actions and behaviors developed by each of the participants through the LINCE PLUS video analysis software and record the data in Excel files in the database created for this purpose. This database will be created in such a way that a code is generated for the participants and no one can identify who the information registered and consigned there corresponds to (except the main researcher) who will save it on their personal computer, on a hard drive to keep copy and in the cloud. These files will be kept with a password, which only the principal researcher will know.

The information and data resulting from the respective analyzes carried out by the evaluator will be sent to the statistician who will proceed to carry out the respective analysis and application of tests in accordance with the data treatment that appears in the data analysis section.

Prior to carrying out the FOCOS test that evaluates the primary and secondary outcomes and, prior to the execution of the tests that evaluate executive functions (exploratory outcome), the following question will be asked to the participants: from 0 to 100, ¿How mentally fatigued are you? Being 0 (not at all fatigued) and 100 (maximum fatigue).

The evaluations of week 1 were carried out on two different days and in the following order: the first day the survey was carried out, mass, height, mental fatigue and finally, the tests were applied to assess the executive functions, for which participants were

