To establish the distribution of the data of the quantitative variables, the Shapiro-Wilk test will be applied. The variables that present a normal distribution will be summarized with means and standard deviation. Variables that present a non-normal distribution will be summarized with medians and interquartile ranges. Likewise, the qualitative variables will be presented in absolute and relative frequency tables.

To establish the behavior of the offensive, defensive, and global IE, a repeated measures design will be carried out that includes 4 evaluations over time (pretest, intermediate test 1, intermediate test 2 and posttest). For this, an ANOVA of repeated measures or the Friedman test will be used according to the normality of the variables, in addition, the assumption of homogeneity of the variances will be evaluated based on the Levene statistic. Since different dependent variables will be evaluated, a multivariate analysis of variance (MANOVA) will also be performed.

For the variables related to executive functions, an intragroup analysis of each of the groups (GE and GC) will be carried out, comparing the pretest and posttest values to establish possible differences, for which the dependent student t test or the Wilcoxon test of according to its distribution. In addition, an intergroup analysis will be carried out to compare the possible differences between the groups (GE and GC), for which the student t test for independent samples or the Mann Whitney U test will be applied according to the distribution of the variables. Similarly, confidence intervals (CI95) and two-tailed effect sizes will be reported, with alpha (α) set to 0.05 and statistical power 0.8 (1- β). The statistical significance value is set at $p \leq 0.05$. An analysis of the information will be carried out using the statistical package SPSS version 27 and the software R free version 4.0. Procedures will be carried out to detect possible inconsistencies in the measurements and to identify outliers and extreme values. Likewise, if necessary, statistical adjustments will be made. Intention-to-treat analysis will be performed.

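### For non-normal IE data the plan prescribes the Friedman test, which has no group term and cannot compare GE with GC

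*Combined protocol and SAP*

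**What the plan says.** The Type of study section describes a parallel trial "with 2 randomized groups (experimental and control", measured at weeks 1, 6, 11 and 16. The Data Collection Procedures section ranks the outcomes: it refers to "the FOCOS test that evaluates the primary and secondary outcomes and, prior to the execution of the tests that evaluate executive functions (exploratory outcome". The IE are therefore the main outcomes and the executive functions are exploratory.

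The Analysis of data section handles the two sets differently.

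- **IE.** For the distribution of quantitative variables, "the Shapiro-Wilk test will be applied". Then, over the four evaluations, "an ANOVA of repeated measures or the Friedman test will be used according to the normality of the variables". Homogeneity of variances is checked with Levene's statistic, and because there are several dependent variables "a multivariate analysis of variance (MANOVA) will also be performed". No factor is named for any of these analyses.
- **Executive functions.** A new paragraph begins: "For the variables related to executive functions, an intragroup analysis of each of the groups (GE and GC) will be carried out". It continues that "an intergroup analysis will be carried out to compare the possible differences between the groups (GE and GC", by independent-samples t test or Mann-Whitney U test. This is the only place where the plan names a GE-versus-GC test.

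**The concern.** The trial asks whether one training programme does better than another. The Friedman test asks whether the four visits differ within players. In the non-normal branch the main outcomes would get an answer to the second question only.

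This matters because IE could well rise in both groups. All players train five times a week, compete at weekends and take FOCOS four times. A common rise can make Friedman significant when the programmes do not differ. Running it separately in each group does not help: it invites the conclusion that the programme works because GE changed significantly and GC did not, which is not a comparison of the groups. If the gap is noticed only at analysis, the between-group test will be chosen after the data have been seen.

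**Working it through.** **1. What the plan was sized for.** The Sample Size Calculation section cites a study and says "they report a mean difference of 1.13 and a standard deviation of 0.81", without naming the variable. The standardised difference is d = 1.13 / 0.81 = 1.395. For two independent groups, two-sided alpha 0.05, the exact t calculation has noncentrality d·√(n/2) and 2n − 2 degrees of freedom. At n = 12 this is 1.395 × √6 = 3.42 with 22 df, giving power 90.4%. The smallest n per group for 80, 85, 90, 95 and 99% power is 10, 11, 12, 15 and 20, which matches all five scenarios. The trial was sized for a between-group comparison.

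**2. What Friedman computes.** With n players, k visits and R_j the sum over players of within-player ranks at visit j:

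Q = [12 / (n·k·(k + 1))] · ΣR_j² − 3n(k + 1)

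For n = 24 and k = 4, Q = 0.025·ΣR_j² − 360, referred to chi-square with 3 df. Group appears nowhere. Two checks confirm this, although both hold by construction:

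- Adding 100 to every GE value in a simulated trial left Q at 1.45 (p = 0.694).
- Reassigning the 24 GE/GC labels at random 1,000 times in another trial left p at 0.124 every time.

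**3. How it behaves.** I simulated 10,000 trials per setting. The assumptions are mine, not the documents': 12 per group, four visits, normal data, equal correlation between visits of 0.3, 0.5 or 0.7, linear change unless stated, significance at p ≤ 0.05. Applying d = 1.395 to IE is also an assumption. Ranges run over the three correlations.

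| Setting | Pooled Friedman | Mann-Whitney on week 16 − week 1 |
|---|---|---|
| No change in either group (check) | 4.6–5.0% | 4.2–4.7% |
| No effect, both rise 0.25 SD | 10–19% | 4–5% |
| No effect, both rise 0.5 SD | 31–65% | 4–5% |
| No effect, both rise 0.75 SD | 65–96% | 4–5% |
| Only GE changes, 1.395 SD | 45–75% | 75–98% |
| Only GE changes, all by week 6 | 54–76% | 75–98% |
| Both rise 0.5 SD, GE a further 1.395 SD | 94–99.9% | 75–98% |
| GE up and GC down by half of 1.395 SD each | 2–3% | 75–98% |

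Pooled Friedman responds to the change common to all 24 players. With a GE-only effect the average change is 1.395 / 2 = 0.70 SD. With opposite changes it is zero, and the test sees almost nothing. At each correlation it rejects more often under no effect with a common 0.75 SD rise (64.9, 78.9, 95.8%) than under a real GE-only linear effect of 1.395 SD (45.4, 58.3, 75.0%).

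Run separately per group with no treatment effect, Friedman gives a significant GE and a non-significant GC in 7–10%, 13–22% and 22–25% of trials, for common rises of 0.25, 0.5 and 0.75 SD.

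**4. Skewed data.** For lognormal data (the exponential of normal data) Friedman's behaviour is the same automatically, because exponentiation preserves within-player ranks. Only the Mann-Whitney results add information: 4–5% under a common 0.5 SD rise and 80–98% under the GE-only linear effect.

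**5. How often the branch is entered.** The plan does not say what Shapiro-Wilk is applied to. For truly normal data, rejection at p ≤ 0.05 would occur in about 5% of trials if one visit is tested, 19% if any of four visits counts, and 32% if any of eight group-by-visit samples counts. The rate for real IE data is unknown.

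**The case against.** The best defence is that this is an omission rather than a wrong test. The IE sentence sets out to describe how the indices behave over time, and Friedman is valid for that. The Levene check suggests that groups are in the ANOVA, the MANOVA is unconditional and can carry group, and the intergroup t/Mann-Whitney sentence runs into statements on alpha, software and intention-to-treat that look study-wide. It may have been meant to cover IE. The defect also operates only if normality is rejected.

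Some of this stands. The ANOVA and MANOVA are incompletely specified, not wrong, and the problem is conditional. But describing behaviour over time does not replace the comparative objective. The MANOVA names no factor and is parametric, so it is no stated remedy once normality has been rejected. The intergroup sentence belongs to a paragraph that opens with executive functions. Even if extended to IE, it names no visit or change score for an outcome measured four times, and the Friedman instruction remains.

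A second objection concerns the effect size. Offensive and defensive IE are averages of success proportions and lie between 0 and 1. A difference of 1.13 exceeds that range, and an SD of 0.81 exceeds the 0.5 maximum for such a variable. The cited figures therefore cannot be in offensive or defensive IE units. That leaves 1.395 as a hypothetical standardised effect only. The label-invariance argument and the no-effect rows of the table do not use it.

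**Conclusion.** The point holds, with high confidence, for the Friedman branch. If normality is rejected, the plan as written applies a test of time to a question about groups, on the outcomes that carry the trial's objective. That conclusion needs no simulation: the group label does not enter the statistic.

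The size is illustrative. With no treatment effect and a common rise of 0.5 SD, pooled Friedman is significant in 31–65% of trials, and separate tests give the misleading GE-only pattern in 13–22%. These figures rest on the assumed correlation, trend shape and size of rise. The randomised data can still answer the question, so this is a fault in the stated analysis, not in the design, but it must be corrected before analysis.

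**What to change.** Remove the Friedman test as the fallback for IE and write, in substance:

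*Offensive, defensive and global IE will each be analysed with group (GE, GC) as between-subject factor, week (1, 6, 11, 16) as within-subject factor, and the group-by-week interaction, which is the comparison of the programmes. If normality fails, GE and GC will be compared by the Mann-Whitney U test on each player's pretest-to-posttest change in that IE.*

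The plan already names the Mann-Whitney test but not change scores, so the change score must be written in. State also what the normality test is applied to, since that decides which branch is used. If Friedman is kept at all, label it a within-group description that supports no conclusion about the programmes.

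The drawback is that this fallback uses only two of the four visits, so weeks 6 and 11 do not enter it.

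The cost is wording and analysis only. FOCOS is already scheduled at all four weeks and SPSS and R are already named, so no extra players or visits are needed. Fix and date the wording before the group codes are opened.

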To obtain the data, the games must be filmed with a camera and later, carry out the respective analyzes and evaluations. In the present investigation, a DJI Fly drone is used, which is positioned 20m high just behind one of the goals, this location guarantees complete visibility of the ATTs executed by the participants and full coverage of the pitch. Once all the corresponding games have been filmed, the videos are downloaded, which are

sent to the video analyst who will carry out the respective analysis and data report in the database created for this purpose. For the analysis, the video analyst will use the LINCE PLUS video analysis software (Soto et al., 2019), which is available and freely accessible.

The FOCOS units of measure are:

Volume, which corresponds to the number of times the soccer player develops tactical behaviors in each category.

The IE is determined through the following formula:

$$IE = \text{Volume of successful tactical behaviors} / \text{Number of tactical behaviors developed in each category of analysis}$$

$$\text{Offensive IE} = \text{Sum of the IE of offensive tactical behaviors} / \text{Number of categories in which the soccer player developed offensive tactical behaviors}$$

$$\text{Defensive IE} = \text{Sum of the IE of defensive tactical behaviors} / \text{Number of categories in which the soccer player developed defensive tactical behaviors}$$

$$\text{Global IE} = \text{Offensive IE} + \text{Defensive IE} / 2$$

The global IE represents the PTK of each soccer player.

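### A normality test chooses between repeated-measures ANOVA and Friedman for each effectiveness index, and the Friedman branch does not compare the two arms

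*Combined protocol and SAP*

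**What the plan says.** The Analysis of data section opens with a distribution check: "To establish the distribution of the data of the quantitative variables, the Shapiro-Wilk test will be applied". For the indices it continues: "To establish the behavior of the offensive, defensive, and global IE, a repeated measures design will be carried out", one that "includes 4 evaluations over time (pretest, intermediate test 1, intermediate test 2 and posttest"). The method then follows from the check: "an ANOVA of repeated measures or the Friedman test will be used according to the normality of the variables". A MANOVA is planned as well, with no stated link to the normality result.

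The text refers to the variables and never to residuals. It does not state:
- whether normality is tested per visit, per arm and visit, or on pooled values;
- what happens if an index passes at three visits and fails at the fourth;
- a significance level for Shapiro-Wilk beyond the general 0.05.

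The Data Collection Procedures section says that the FOCOS test, which yields the three indices, covers the primary and secondary outcomes. Of the global index the plan says: "The global IE represents the PTK of each soccer player".

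**The concern.** The pretest does more than pick between two routes to the same answer. A repeated-measures ANOVA can carry group and group-by-visit terms, so it can address whether GE and GC differ. The classical Friedman test ranks each player's visits against each other and tests whether the visits differ. Run on all players, or within each arm, it contains no GE–GC comparison. The plan specifies a between-group test (t or Mann-Whitney) for executive functions but none for the indices on the Friedman branch.

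A Shapiro-Wilk rejection, including one due to chance alone, can therefore remove the randomised comparison for an index and leave only the MANOVA. That is a joint test over several dependent variables and does not by itself give an effect estimate for a single index. Because the choice is made index by index, global IE could also be reported by a different method from the two components it is calculated from.

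**Working it through.** **Inputs from the documents.** 24 players, 12 per arm; four visits; three indices; global IE taken as the mean of offensive and defensive IE; general alpha 0.05.

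**Assumptions.** Shapiro-Wilk is also judged at 0.05. An index leaves ANOVA if any of its normality tests rejects. Between-visit correlation runs from 0 to 0.9 and offensive–defensive correlation from 0 to 0.8; the documents give neither.

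**Step 1: the plan's own figure.** The Sample Size Calculation section cites an earlier study: "they report a mean difference of 1.13 and a standard deviation of 0.81". So d = 1.13/0.81 = 1.395. A two-sample t-test (noncentral t, two-sided 0.05) gives 10, 11, 12, 15 and 20 per arm for 80, 85, 90, 95 and 99% power. All five scenarios reproduce, and power at 12 per arm is 0.904. The chosen one is "Scenario 3 (90% power): (24 soccer players. GE = 12 and GC = 12"). A normality test would thus see 24 values per visit, or 12 per arm and visit. The documents give no switching rate to reproduce.

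**Step 2: simple arithmetic.** With k independent tests at 5% on normal data, P(at least one rejection) = 1 − 0.95^k.
- One index, 4 visits: 1 − 0.95^4 = 18.5%. One index, 4 visits × 2 arms: 1 − 0.95^8 = 33.7%.
- Three indices: 14.3% (k = 3), 46.0% (k = 12), 70.8% (k = 24).

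The tests are correlated, so the true rates should generally be somewhat lower.

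**Step 3: simulation.** Multivariate normal data, no departure from normality. Chance that at least one of the three indices leaves ANOVA:

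| Reading of the rule | Correlations 0.5 (visits) and 0.3 (offensive–defensive), 4,000 trials | All correlations tried |
|---|---|---|
| One test per index, ANOVA residuals | 10.5% | 8–12% |
| One test per index, single visit | 14.1% | 10–15% |
| One test per index, all 96 raw values | 19.7% | 11–78% |
| Each visit, arms pooled (12 tests) | 44.3% | 28–48% |
| Each visit in each arm (24 tests) | 66.5% | 51–71% |

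The third row climbs with between-visit correlation because it treats four values from one player as independent. For the last two rows, moderate correlations (0.5 to 0.7 between visits, 0 to 0.3 between offensive and defensive) give about 42–45% and 64–69% across repeated runs. The lowest value in any run of those two readings was 27%.

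For global IE alone the rate is about 18% (each visit) or 29–34% (each visit in each arm), in line with Step 2.

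**Step 4: mixed methods.** At correlations 0.5 and 0.3, the three indices ended on different methods in about 43% (each visit) and 61% (each visit in each arm) of trials, so most switches split the set.

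**Step 5: what Friedman detects.** Let both arms improve equally, rising steadily to 1 SD by the last visit, with between-visit correlation 0.5. The GE–GC difference is then zero, yet Friedman on all 24 players rejects in 97% of trials. A significant result on that branch says nothing about the intervention.

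**The case against.** **The switching rate is not a property of the plan.** A reader might infer that the plan would switch an index in 42% to 67% of trials. The documents do not support that. They prescribe neither 12 nor 24 tests, nor that a single rejection decides, nor a pretest alpha. One test per index on residuals gives about 10%. This stands, so the figure must be given by reading. The residual reading does fit poorly with text that speaks only of variables.

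**It is not an error rate.** A reader might infer inflated type I error. None was computed for the indices. For the parallel t or Mann-Whitney choice in executive functions, the two-stage error was 5.2–5.5%, close to nominal. The case here rests on the changed question, not on inflation.

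**The pretest is not shown to miss skew.** A reader might add that Shapiro-Wilk is weak with 12 players. One such test does usually miss a lognormal with log-SD 0.5. Under the any-rejection rule behind the higher rates, however, that same distribution is caught in about 80–98% of trials. The two arguments cannot be combined.

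**The choice is partly fixed in advance.** Both branches and the selecting test are named beforehand, the statistician is masked to group, and the MANOVA runs regardless. That limits the scope for picking a favourable result. It does not restore a GE–GC estimate for an index that goes to Friedman.

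**The indices are not all primary.** For one index the rates are lower, as shown for global IE.

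**Conclusion.** The concern holds in a limited form. A normality result on the raw variables chooses the analysis separately for each index by an undefined rule, and one of the two branches does not address the randomised comparison.

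With exactly normal data, at least one index is switched in about 8–15% of trials (one test per outcome, on residuals or at one visit), 42–45% (each visit) or 64–69% (each visit in each arm). The last two readings span 27–71% over the wider range of assumed correlations. That the answer varies this much with an unwritten rule is itself the finding. The figures rest on a pretest alpha of 0.05, any rejection triggering the switch, and assumed correlations. No loss of power or inflation of error is claimed. This is a cheap improvement, not a defect that invalidates the trial.

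**What to change.** In the Analysis of data section:
- Drop Shapiro-Wilk as the selector for the indices. It may stay for choosing mean/SD or median/IQR in descriptive tables.
- Analyse offensive, defensive and global IE with the same linear repeated-measures model: group, visit (weeks 6, 11 and 16), group-by-visit, and the pretest value as baseline covariate. State the covariance structure.
- Name the week-16 GE–GC difference, with its 95% confidence interval, as the main contrast.
- Check the residuals of that model.
- As sensitivity analysis, give a permutation p-value for the same contrast, re-assigning arms as randomised, that is, within the permuted blocks of 4 and 6.

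The cost is a paragraph of analysis wording and a short script in R, which the plan already names. Design, sample size and data collection do not change.

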All the previously mentioned tests to evaluate executive functions are carried out both at the beginning and at the end of the interventions, they last approximately between 50 and 60 minutes and they are coordinated by the neuropsychologist, applying the protocols of each one of them. All these tests will be carried out at the IUEFD of the UdeA.

To evaluate the sociodemographic characteristics of the population, a survey is applied with simple questions to determine age, sporting age, playing position, socioeconomic stratum, and educational level. This survey is carried out by one of the researchers at the beginning and at the end of the interventions and is carried out at the IUEFD. If necessary, supporting documents will be requested such as an identity document, study certificate or degree certificate, and utility bill for the home.

Anthropometric Variables

Mass. It was measured using a bioelectrical impedance balance, brand Omron® HBF-510 (Bannockburn, IL, USA), which has a sensitivity of 100 grams. The participants were

measured in resting conditions, free of clothes and shoes (shorts only) and without carrying any metallic object (electronic devices, keys, jewelry, watches, piercing).

Size. It was measured using a stadiometer, Seca 213, with a sensitivity of 1 millimeter. The participants were measured in resting conditions, free of clothes and shoes (only in shorts). The mass and height evaluations were carried out by a researcher trained in sports training and familiar with the use of scales and stadiometers. The measurements are made both at the beginning and at the end of the interventions and they are carried out in the Integrated Laboratory of Physical Activity and Sports Sciences (LICAFDE).

Body Mass Index (BMI). It will be found by calculating the formula mass/height^2 (kg/m^2). The BMI calculations will be made both at the beginning and at the end of the interventions with the respective data that shows the mass and height.

Pilot Testing Procedures

Several pilot tests were carried out to familiarize and sensitize all the people involved in the study (soccer players, coaches, researchers, and assistants). Likewise, it is important that everyone knows the people with whom they are going to interact, the places of training and evaluation, the contexts, norms, and regulations that must be complied, procedures and protocols for evaluation and intervention, equipment, technology, software, materials, and clothing to use.

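### Executive functions are to be tested within each arm as well as between arms, and the plan does not say that only the between-arm comparison supports conclusions about the programme

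*Combined protocol and SAP*

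**What the plan says.** The protocol's objectives include the effect of the training programme on executive functions. Data Collection Procedures labels these outcomes exploratory. They are measured twice, in week 1 and week 16: "All the previously mentioned tests to evaluate executive functions are carried out both at the beginning and at the end of the interventions".

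For these variables the Analysis of data section plans two analyses:

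- Within arms: "an intragroup analysis of each of the groups (GE and GC) will be carried out", "comparing the pretest and posttest values to establish possible differences", by paired t test or Wilcoxon test.
- Between arms, in the next sentence: "the student t test for independent samples or the Mann Whitney U test will be applied", according to distribution.

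Confidence intervals and effect sizes are to be reported, and significance is set at p ≤ 0.05 for everything. The section does not say which analysis supports a conclusion about the programme. It also does not say whether the between-arm test compares week-16 values or changes, or whether it adjusts for the week-1 score. The general remarks on controlling confounders and on making adjustments if necessary do not name the baseline score.

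**The concern.** The objective is causal, and a within-arm change cannot answer it. The same battery is repeated after about 15 weeks, and both arms train five times a week and compete at weekends in between. A gain in the experimental arm (GE) is therefore the sum of the programme's effect, practice on the tests, and whatever the season does to all players. The control arm (GC) is there to remove the last two.

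Placing the two within-arm p-values side by side does not repair this. A significant result in one arm and a non-significant result in the other is not a test of the difference between arms. With 12 players per arm, such splits can be common when the arms change identically. If the within-arm and between-arm results disagree, the plan has no rule for which prevails, and an improvement seen only in GE could be reported as a finding on executive functions.

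**Working it through.** **Inputs.** From Sample Size Calculation: 12 per arm, mean difference 1.13, SD 0.81. From Analysis of data: two-sided, alpha 0.05. The documents give no expected change, variability or pre–post correlation for any executive-function score, so the size of the change common to both arms is an assumption, shown over a range.

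**The plan's own figure.** For a two-sample t test with standardised difference 1.13/0.81 = 1.395, the totals needed for 80, 85, 90, 95 and 99% power are 20, 22, 24, 30 and 40. All five of the plan's scenarios are reproduced. Power at 12 per arm is 90.4%. The 12 per arm is therefore sound on its stated inputs, but those inputs do not concern executive functions.

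**Within-arm tests when the arms do not differ.** Let δ be the true change in both arms, in SDs of the change score.

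- The paired t statistic has 11 degrees of freedom, critical value 2.201 and noncentrality δ√12.
- Let U be the chance of a significant improvement in one arm, and P the chance of significance in either direction.
- The arms are independent, so P(exactly one arm significant) = 2P(1 − P).
- P(significant improvement in GE, nothing significant in GC) = U(1 − P).

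| δ (assumed) | P | Exactly one arm significant | Improvement in GE alone |
|---|---|---|---|
| 0 | 0.050 | 9.5% | 2.4% |
| 0.3 | 0.158 | 26.6% | 13.2% |
| 0.5 | 0.353 | 45.7% | 22.8% |
| 0.6 | 0.475 | 49.9% | 24.9% |
| 0.8 | 0.714 | 40.9% | 20.4% |
| 1.0 | 0.883 | 20.7% | 10.3% |
| 1.2 | 0.965 | 6.7% | 3.4% |

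Two rows worked through:

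- δ = 0: 2 × 0.05 × 0.95 = 0.095, and 0.025 × 0.95 = 0.024.
- δ = 0.6: 2 × 0.475 × 0.525 = 0.499, and 0.475 × 0.525 = 0.249.

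The first percentage column counts either arm, in either direction. The last column is the one that matches a claim of improvement only in GE.

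**Between-arm test on the same data.** In simulated trials with identical arms, the independent t test on change scores rejects in about 5% of trials, whatever the common change. At δ = 0.6 it is significant in only about 9% of the trials in which the within-arm tests split. The two planned analyses would then usually disagree, and the between-arm one holds its error rate.

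**The case against.** The strongest reply is that the plan already contains the right analysis. The between-arm test stands in the next sentence, with intervals and effect sizes, and it keeps its 5% error rate. The verb in the quoted phrase is routine in this document and refers there only to pretest against posttest values. The outcomes are exploratory, and the tactical-knowledge outcomes are not affected. All of this stands and limits the weight of the point. It does not remove it: the within-arm tests are planned hypothesis tests at the same significance level, listed first, with no statement that they are descriptive.

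Three stronger readings are tempting but not supported:

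- A reader might infer that programme effects are to be judged from the within-arm tests instead of the between-arm test. The text plans both, and nowhere says that significance in one arm only will be read as an effect. The risk comes from silence on which analysis governs.
- A reader might take 41–50% as the chance of a false claim in favour of GE. It counts either arm in either direction and applies only near the worst range of common change. Improvement in GE alone is 20–25% there and 2.4% with no change.
- A reader might multiply over the battery and conclude that at least one split is nearly certain. That needs independent scores, yet several scores come from one task. It also needs a fixed number of scores, and Table 1 and the test descriptions do not list the same ones.

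**Conclusion.** The point holds as a matter of which analysis carries the inference. The plan tests executive functions within each arm beside the between-arm comparison, and does not reserve conclusions about the programme for the latter. If the arms truly change alike, the within-arm results split in 9.5% of scores with no change, 27–50% at common changes of 0.3–0.8 SD, and 7% at 1.2. Improvement significant in GE alone runs from 2.4% up to 25% and back to 3% over the same range.

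These figures assume 12 analysed players per arm, normally distributed changes with equal spread, and t tests. Wilcoxon tests were not calculated. That a within-arm change cannot isolate the programme needs none of these assumptions. Because the outcome is exploratory and a valid between-arm test is already planned, this is a worthwhile correction of wording and not a threat to the trial's main result.

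**What to change.** In the executive-function paragraph of Analysis of data:

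1. Drop the within-arm hypothesis tests. Report within-arm change as description only: mean and SD, or median and interquartile range. Removing p-values but keeping a per-arm 95% CI would not be enough, because that interval excludes zero exactly when the paired t test is significant, so the same split would reappear.
2. State that conclusions on executive functions rest solely on the between-arm difference and its 95% CI.
3. Define that difference: the week-16 score compared between arms with adjustment for the week-1 score (ANCOVA) or, at minimum, a comparison of change scores.

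This needs no extra players, visits or measurements. The only loss is that within-arm p-values are no longer reported.
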